4.3.3. Exploratory Efficacy Evaluations

The continuous exploratory endpoints including grip strength, SGNFD, IENFD, dermal amyloid content, EQ-5D-5L index, EQ VAS, original NIS+7 and small/large fiber function (defined in Appendix 7.2.1) will be analyzed using an MMRM model similar to those employed for the primary analysis.

The categorical exploratory endpoints PND score and FAP stage will be descriptively summarized by presenting the number and percentage of patients in each category for each visit. The number of percentage of patients with improving, no change, and worsening in PND/FAP at each visit will also be summarized.

For EQ-5D-5L, a categorical summary of the numbers and percentages of patients reporting each ordinal response within each EQ-5D domain will be presented.

Cardiac structure and function will be assessed for all patients through echocardiograms. Cardiac stress and injury will be measured using serum levels of the cardiac biomarkers NT-proBNP and troponin I. Quantification of these biomarkers will be performed at a central laboratory. Descriptive statistics will be provided for actual values, changes, and percentage changes from baseline in echocardiogram parameters, serum levels of troponin I and NT-proBNP by treatment arm.

For cardiac subpopulation (defined in Section 4.2), the change from baseline to Month 18 in LV wall thickness, LV mass, LVEF, LV longitudinal strain, NT-proBNP and troponin I will be compared between the 2 treatment arms using MMRM. The model will include baseline value

as covariate and fixed effect terms including treatment arm, visit, and treatment-by-visit interaction.

All echocardiogram and cardiac function biomarkers data will be presented in data listings.

MR neurography data will be presented in a data listing.

4.3.4. Subgroup Analyses

Subgroup analyses will be conducted to assess the consistency of treatment effect within various subgroups defined by the following baseline characteristics:

- Age [≥ 65 ; < 65 at randomization]
- Sex [Male; Female]
- Race [White; Non-White]
- Region [North America; Western Europe; Rest of World]
- NIS [< 50 ; ≥ 50]
- Genotype Class [Early-onset V30M; Other]
- Previous Tetramer Use [Yes; No]
- Genotype [V30M; non-V30M]
- FAP Stage [I; II & III]

Subgroup analyses will be performed for the primary endpoint mNIS+7 and Norfolk QOL-DN using MMRM models with baseline mNIS+7 score as a continuous covariate and genotype (V30M vs. non-V30M) as a factor. A forest plot will be generated to illustrate the estimated treatment effect along with 95% CI within each subgroup.

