4.3.2. Secondary Efficacy Evaluations

Secondary efficacy endpoints include Norfolk QOL-DN total score, NIS-W, R-ODS, 10-meter walk test speed, mBMI, and COMPASS-31. To control overall type I error, these endpoints will be tested in a hierarchical order as described in Section 3.6.

All the secondary endpoints are assessed at baseline, Month 9, and Month 18 with the exception of mBMI. mBMI is assessed at baseline, Day 84, Day 189, Day 357, Day 462 and Day 546. Day 546 will be used as Month 18 assessment.

For 10-meter walk test, the walk speed for patients unable to perform the walk will be imputed as 0. The change from baseline will then be calculated as 0 – baseline walk speed.

Change from baseline at Month 18 in the secondary efficacy endpoints will be analyzed for the mITT population, using an MMRM model similar to the model described for the primary analysis of mNIS+7 while adjusting for baseline value of the endpoint being modeled. For these secondary endpoints (except NIS-W), MMRM model will also include baseline NIS (< 50 vs. ≥ 50) as a factor. The MMRM model for NIS-W will not include baseline NIS since baseline NIS-W will be included as a covariate in the model.

For the first secondary endpoint Norfolk QOL-DN Total Score, the MMRM method will also be conducted for the PP population. In addition, sensitivity analyses will be conducted using ANCOVA/MI and including data post alternative treatment for FAP similar as described for mNIS+7 (see Section 4.3.1.3).

Month 18 change from baseline in mBMI will be estimated from the MMRM model using assessment results from all time points.

The planned analyses of the secondary endpoints are summarized in [Table 2](#).

Table 2 Analysis of Secondary Endpoints

Endpoint	Statistical Method	Analysis Population	Special Notes
Norfolk QOL-DN total score	Primary analysis: MMRM	mITT	
	Sensitivity analysis: 
 • MI/ANCOVA • MMRM - including Data Post Alternative Treatment for FAP 	mITT	
	Other analysis: MMRM	PP	
NIS-W	MMRM	mITT	Excludes data post alternative treatment for FAP
R-ODS	MMRM	mITT	
10-meter walk test speed	MMRM	mITT	For patients unable to perform the walk, walk speed imputed as 0
mBMI	MMRM	mITT	Measured at baseline, Day 84, Day 189, Day 357, Day 462 and Day 546
COMPASS-31	MMRM	mITT	

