5.4. Adjustment for Covariates in Statistical Models

The table below summarizes the history of changes in baseline covariates used in the statistical models.

Baseline Covariates	Protocol	SAP V1.0	SAP V2.0
	ANCOVA	ANCOVA	MMRM/ANCOVA
Baseline mNIS+7	X	X	X
Genotype (V30M vs. Non-V30M)	X		X
Genotype class (early onset V30M vs. Other)		X	
Age at hATTR symptom onset (< 50 vs. ≥ 50)			X
Previous tetramer stabilizer use (Yes vs. No)	X	X	X
Region (Western EU, North America, Rest of World)			X
Age at study entry as continuous variable	X		

Genotype class (early onset V30M vs. other) is one of the stratification factors at randomization. The early onset V30M subgroup includes patients who have the V30M genotype and were younger than 50 years old at hATTR amyloidosis symptom onset. At the time of this SAP amendment, the enrollment was complete and there were only 23 early onset V30M patients. Given the small sample size, the composite covariate “genotype class” is decomposed into 2 separate covariates “genotype” and “age at hATTR amyloidosis symptom onset.”

Region is added as a covariate because different rates of attrition and disease worsening were observed for different regions during blinded data monitoring. In addition, adding region may potentially address the influence of different non-V30M types observed across regions.

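### SAP 4.3.4 names baseline mNIS+7 as the only continuous covariate for the Norfolk QOL-DN subgroup models; read literally, they leave out baseline Norfolk

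*SAP*

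**What the plan says.** Section 4.3.4 of the SAP covers both subgroup endpoints in one sentence: "Subgroup analyses will be performed for the primary endpoint mNIS+7 and Norfolk QOL-DN using MMRM models with baseline mNIS+7 score as a continuous covariate". The sentence ends by naming genotype as the single factor ("as a continuous covariate and genotype (V30M vs. non-V30M) as a factor"). It names no baseline Norfolk term. The results go to a forest plot whose stated purpose is to judge whether the treatment effect is consistent across subgroups.

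Other models in the SAP keep the endpoint's own baseline:

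- **Main Norfolk model (4.3.2).** It is "similar to the model described for the primary analysis of mNIS+7 while adjusting for baseline value of the endpoint being modeled". Neuropathy severity is an addition: "For these secondary endpoints (except NIS-W), MMRM model will also include baseline NIS", dichotomized at 50.
- **NIS-W (4.3.2).** "The MMRM model for NIS-W will not include baseline NIS since baseline NIS-W will be included as a covariate in the model". Here the endpoint's own baseline is the reason for leaving severity out.
- **Cardiac subpopulation (4.3.3).** This is the SAP's shortest efficacy model, with only treatment, visit and their interaction as fixed effects. It still states "The model will include baseline value".

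The covariate history table in section 5.4 lists baseline mNIS+7 as the only baseline score. It contains no rule for Norfolk or for subgroups.

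**The concern.** A programmer who follows 4.3.4 to the letter would fit the Norfolk subgroup models with a neuropathy composite in place of the patient-reported score's own baseline. The SAP gives no reason for this. A wish for a smaller model does not explain it, because the even shorter cardiac model keeps its own baseline.

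The overall Norfolk estimate and the subgroup Norfolk estimates would then condition on different baseline scores, in a display meant to show consistency. Some subgroups are small: section 5.4 reports that "there were only 23 early onset V30M patients". In a group of that size the arms can differ noticeably at baseline by chance, so the form of the baseline adjustment can visibly move the point estimate. Norfolk is the first secondary endpoint and the only secondary endpoint given subgroup analyses.

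**Working it through.** The plan states no figure that depends on this point, so there is none to reproduce. The textual finding comes from setting 4.3.4 beside 4.3.2, 4.3.3 and 5.4. The arithmetic below only sizes the consequence, and **every correlation and SD ratio in it is assumed**.

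**Set-up.** Let B be baseline Norfolk (SD 1), Y Month 18 Norfolk (SD k), M baseline mNIS+7 (SD 1), and C = Y − B. Let corr(B,Y) = rho, corr(M,B) = r and corr(M,Y) = s. The outcome is taken to be change from baseline, as in the main model; 4.3.4 does not say. The calculation is a single-visit ANCOVA, a simplification of the two-visit MMRM.

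- Var(C) = k² + 1 − 2·k·rho
- Var(C given B) = Var(C) − (k·rho − 1)²
- Var(C given M) = Var(C) − (k·s − r)²

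Using M in place of B therefore loses precision exactly when |k·rho − 1| > |k·s − r|.

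**1. M acts only through B (s = rho·r).** At k = 1.0, rho = 0.7, r = 0.5, we have s = 0.35:

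- Var(C) = 1 + 1 − 1.4 = 0.600
- given B: 0.600 − 0.3² = 0.510
- given M: 0.600 − (0.35 − 0.5)² = 0.5775
- SE ratio = √(0.5775/0.510) = 1.064

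The grid takes rho from 0.5 to 0.9 and k from 1.0 to 1.25 in steps of 0.05, and r from 0 to 0.8 in steps of 0.1 (9 × 6 × 9 = 486 points). The SE ratio runs from 1.000 (k 1.25, rho 0.8) to 1.155 (k 1.0, rho 0.5, r 0), with median 1.027. It is below 1.05 at 71% of points.

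**2. That assumption relaxed.** The sign is then not fixed.

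| k | rho | r | s | Variance given B | Variance given M | SE ratio |
|---|---|---|---|---|---|---|
| 1.25 | 0.8 | 0.5 | 0.5 | 0.5625 | 0.547 | 0.986 |
| 1.25 | 0.8 | 0.5 | 0.6 | 0.5625 | 0.500 | 0.943 |
| 1.0 | 0.7 | 0.5 | 0.45 or 0.55 | 0.510 | 0.5975 | 1.082 |

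**3. Direction of the imbalance error.** In a change score, baseline Norfolk is already subtracted with coefficient 1. Under assumption 1 the coefficient that removes the imbalance is k·rho. If k·rho < 1, the change score over-corrects. Of the 9 × 6 = 54 (rho, k) pairs, 48 (89%) have k·rho below 1, 1 (2%) has it equal to 1, and 5 (9%) have it above 1. These are shares of an assumed grid, not probabilities.

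**4. Size of the imbalance error.** Take the 23 early-onset V30M patients with an assumed 15:8 split, close to 2:1.

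- SD of the between-arm difference in mean B: √(1/15 + 1/8) = 0.438
- SD of the resulting shift: |k·rho − 1| × 0.438 × √(1 − r²)
- k 1.0, rho 0.7, r 0.5: 0.3 × 0.438 × 0.866 = 0.114
- k 1.0, rho 0.5, r 0: 0.5 × 0.438 = 0.219
- k 1.25, rho 0.8: 0

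Units are baseline Norfolk SDs. The shift is random around zero, because randomization makes the expected imbalance zero. In a simulation of the single-visit model (15:8, 20,000 runs), the mean estimate under the null stayed within 0.005 SD of zero for every model.

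**The case against.** The strongest reply is that 4.3.4 is not a complete model statement. It also names no treatment arm, visit, interaction, covariance structure or outcome. It must therefore borrow from 4.3.1.1 and, for Norfolk, from 4.3.2, where the rule is "while adjusting for baseline value of the endpoint being modeled". The SAP uses mNIS+7 as a template elsewhere too: the 5.4 table lists only that score, and the Norfolk multiple-imputation analysis is defined by reference to the mNIS+7 description. Shorthand is a plausible explanation, and a reader should not infer that the sponsor deliberately dropped baseline Norfolk. What remains is that 4.3.4 gives its own reduced covariate list, names the wrong score for one of its two endpoints, and is not corrected anywhere.

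A second reply is that the two Norfolk models would differ even after the edit. This is right. The main model also carries baseline NIS, age at symptom onset, region and previous stabilizer use, and 4.3.4 names none of them. Dropping factors in small subgroups is a defensible simplification. Replacing an endpoint's own baseline with another instrument's score is a different matter.

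A third reply is that the magnitude rests wholly on assumptions and has no fixed sign. This also stands. The point rests on the wording, not on a demonstrated loss of precision.

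**Conclusion.** The point holds as a wording defect of low severity. As written, 4.3.4 gives the Norfolk subgroup models baseline mNIS+7 and no baseline Norfolk; confidence in that reading of the text is high. What the sponsor intended cannot be settled from the documents.

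Under assumed correlations the standard error would be 0 to 15% larger (median about 3%) if baseline mNIS+7 acts only through baseline Norfolk. In the relaxed cases shown it ranges from 6% smaller to 8% larger. In a 23-patient subgroup the random shift has an SD of about 0.11 baseline SD in the central case, and 0 to 0.22 across the cases shown.

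Three stronger conclusions that a reader might draw are not supported:

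- **Biased subgroup estimates.** The shift is random around zero.
- **Imbalance left only partly adjusted.** With a change-score outcome, the error under most of the assumed values is over-correction.
- **Harm to the trial's conclusions.** The subgroup analyses are descriptive and sit outside the testing hierarchy, so no alpha is involved and the main Norfolk result is untouched.

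**What to change.** In 4.3.4, replace the reference to the baseline mNIS+7 score with each endpoint's own baseline as the continuous covariate: baseline mNIS+7 for mNIS+7 and baseline Norfolk QOL-DN for Norfolk. The wording of 4.3.2 can be reused. If baseline mNIS+7 is also wanted in the Norfolk subgroup models, add it alongside baseline Norfolk, as 4.3.2 does with baseline NIS. It would help to state in the same sentence that the outcome is change from baseline.

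The cost is one phrase of SAP text before unblinding. Baseline Norfolk is already collected and already used in the main model. The edit aligns the baseline score with 4.3.2 and does not make the models identical. If the present text was shorthand, the edit only removes the ambiguity.

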4.3.5. Component Analyses

Component analyses will be conducted to assess the consistency of treatment effect on the change from baseline at Month 18 for each of the component of mNIS+7 including NIS-W, NIS-R, QST, $\sum 5$ NCS, and postural blood pressure. The analyses will be performed using MMRM models similar to those employed for the primary analysis. A forest plot will be generated to illustrate the estimated treatment effect along with 95% CI for each component.

4.4. Pharmacodynamic Analyses

The PD parameters include serum TTR (ELISA), serum TTR (turbidimetric assay), RBP, and vitamin A. All summary tables and figures will be based on assessments within 21 days of last dose of study drug. Assessments more than 21 days after last dose will be presented in listings and individual patient plots only.

Summary tables will be provided for observed values, changes and percentage changes from baseline for each scheduled time point by treatment arm.

For serum TTR (ELISA), the maximum percentage reduction and mean percentage reduction over 18 months will be summarized using descriptive statistics. Subgroup analysis will be provided for age (≥ 65 vs. < 65), sex (male vs. female), genotype (V30M vs. Non-V30M), and previous tetramer stabilizer use (yes vs. no).

For vitamin A and RBP, the mean percentage reduction over 18 months will be summarized using descriptive statistics.

The correlation coefficient and p-value based on mixed model will be calculated to assess the correlation between the changes from baseline in ELISA TTR versus Turbidimetric TTR. A scatterplot will be provided to visualize the data.

The therapeutic hypothesis for patisiran is that TTR reduction will result in clinical benefit in hATTR patients. The inter-patient variability in the degree of TTR reduction provides an opportunity to examine the relationship of TTR reduction to clinical endpoints. TTR reduction 22 days after the first dose of Patisiran as the first TTR assessment timepoint and prior to the second dose, will be used for analysis of the correlation between TTR reduction and change in mNIS+7 because this time point reduces the impact of missed doses or missed TTR assessments over 18 months of dosing. Pearson correlation coefficients and 95% confidence intervals will be calculated for Day 22 TTR % reduction and mNIS+7 total score change from baseline at the 9- and 18-month time points, for patisiran arm and placebo arm separately. Scatterplots will be provided to visualize the data.

All PD data will be displayed in data listings.

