3.2. General Methods

All data listings that contain an evaluation date will contain a study day relative to the day of the first dose of study drug, which is designated as Day 1. On-treatment study days will be calculated as evaluation date – first dose date +1 and pre-treatment days will be calculated as evaluation date – first dose date. For example, the day prior to study drug administration will be Day -1, the first dose day of study drug will be Day 1 and the day after the first dose of study drug will be Day 2, etc.

All output will be incorporated into Microsoft Word files, sorted and labeled according to the International Conference on Harmonisation (ICH) recommendations, and formatted to the appropriate page size(s).

For categorical variables, summary tabulations of the number and percentage of patients within each category (with a category for missing data) of the parameter will be presented. For continuous variables, the number of patients, mean, median, standard deviation (SD), minimum, and maximum values will be presented.

Laboratory data (including vitamin A and RBP) collected and recorded as below the limit of detection will be set equal to the lower limit of detection for the calculation of summary statistics.

For assessments that are repeated multiple times on the study day (e.g., 10-meter walk tests, IENFD, SGNFD, etc.), the average will be calculated unless otherwise noted.

Formal statistical hypothesis testing will be performed on the primary and secondary efficacy endpoints with all tests conducted at the nominal 2-sided 0.05 level of significance. Secondary endpoints will be tested in a prespecified hierarchy (Section 3.6). Summary statistics will be presented, as well as 2-sided 95% confidence intervals on selected parameters, as described in the sections below.

All summaries will be presented by treatment arm. All data recorded on the CRF will be included in data listings.

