4.3.1.1. Primary Analysis using MMRM Method for the mITT Population

The primary analysis will be performed using a restricted maximum likelihood (REML) based MMRM approach. The outcome variable is change from baseline in mNIS+7. The model includes baseline mNIS+7 score as a continuous covariate and fixed effect terms including treatment arm, visit (Month 9 or Month 18), treatment-by-visit interaction, genotype (V30M vs. non-V30M), age at hATTR Symptom onset (< 50 ; ≥ 50), region (North America, Western Europe, and Rest of World), and previous tetramer stabilizer use (yes vs. no). An unstructured covariance structure will be used to model the within-patient errors. The Satterthwaite approximation will be used to estimate the degrees of freedom. The primary comparison is the contrast (difference in least squares means [LS means]) between the patisiran and placebo groups at 18 months. Analysis will be implemented with SAS PROC MIXED.

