4.5.2. Statistical Methods

Descriptive statistics for plasma PK parameters will include the number of patients, mean, SD, coefficient of variation (CV), median, minimum, maximum, geometric mean and geometric CV%.

The plasma C_{max}, C_p (30min) and C_{trough} of ALN-18328 (siRNA), DLin-MC3-DMA and PEG₂₀₀₀-C-DMG will be summarized by nominal sampling day. Urinary amounts of ALN-18328 and 4-dimethylaminobutyric acid recovered will be estimated as urine concentration

times the associated urine volume and will be summarized by nominal sampling day. Mean concentrations (+/- SD) will be plotted versus nominal sampling time.

Steady-state PK parameters for ALN-18328 (siRNA), DLin-MC3-DMA and PEG₂₀₀₀-C-DMG will be summarized overall and by subgroup (gender, anti-drug antibody status).

Plasma concentration data will be presented in by-patient listings.

The PK-PD relationship between the plasma concentration of ALN-18328 and the percent change from baseline in TTR protein, vitamin A and RBP will be explored graphically.

The PK exposure-response relationships for the primary endpoint (mNIS+7), TTR, and incidence of relevant AEs may also be explored. These may be summarized by ALN-18328, DLin-MC3-DMA and PEG₂₀₀₀-C-DMG PK exposure quartiles at 18-months (Day 546).

Population PK and exposure-response modeling will be reported separately.

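### The exploratory TTR–outcome correlation in SAP 4.4 is unadjusted, although degree of TTR reduction is not randomised within an arm; an adjusted slope should sit beside it

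*SAP*

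**What the plan says.** SAP 4.4 opens this part with the reasoning behind the drug: "The therapeutic hypothesis for patisiran is that TTR reduction will result in clinical benefit in hATTR patients". It then says that variation between patients in the degree of TTR reduction "provides an opportunity to examine the relationship of TTR reduction to clinical endpoints". The tool is given in one sentence: "Pearson correlation coefficients and 95% confidence intervals will be calculated for Day 22 TTR % reduction and mNIS+7 total score change from baseline", at the two efficacy time points, "for patisiran arm and placebo arm separately", with scatterplots. No covariate, partial correlation or regression is mentioned, and no p-value or decision rule is attached.

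Three other places bear on it:

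- **SAP 4.3.1.1** (primary MMRM). "The model includes baseline mNIS+7 score as a continuous covariate and fixed effect terms"; those terms include genotype, age at symptom onset, region and previous tetramer stabilizer use.
- **SAP 3.2** (scope of testing). "Formal statistical hypothesis testing will be performed on the primary and secondary efficacy endpoints with all tests conducted at the nominal 2-sided 0.05 level". The correlation is neither.
- **SAP 4.5.2** (exposure-response). "The PK exposure-response relationships for the primary endpoint (mNIS+7), TTR, and incidence of relevant AEs may also be explored", possibly by quartiles of PK exposure. Exposure-response modelling is to be reported separately; no covariates are given.

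**The concern.** Randomisation makes the two arms comparable. It does not make patisiran patients with a large Day 22 reduction comparable to patisiran patients with a small one. Computing the correlation by arm removes confounding by treatment but not by patient characteristics.

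The plan treats five baseline factors as relevant to mNIS+7 change by putting them in the primary model. SAP 5.4 adds that region went in partly because worsening differed between regions under blinded monitoring. SAP 4.4 also plans to summarise TTR reduction over 18 months by age, sex, genotype and previous stabilizer use. Genotype and stabilizer use are therefore on both lists. If any such factor is related to both variables, the raw coefficient mixes that factor with the relation of interest.

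At stake is the reading of an exploratory mechanistic result. A reported 95% interval will be read for whether it excludes zero, and this is the only firmly specified analysis that links degree of TTR reduction to clinical outcome.

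**Working it through.** **Inputs from the documents.** SD 16, difference 8.95, 90% power, two-sided 0.05, 154 evaluable, 25% discontinuation, about 200 enrolled (SAP 3.1); 2:1 allocation (SAP 1.2.2). There is no stated figure for the correlation. The sample-size figures serve only to set the number per arm.

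**Reproducing the plan's figure.** Placebo n = (1 + 1/2) × [16 × (1.960 + 1.282) / 8.95]² ≈ 50.4, so 51, and 153 in total against the stated 154. The noncentral t with 51 and 103 gives 90.1% power. 154 / 0.75 gives 206, consistent with about 200. Working back, 200 × 0.75 = 150 evaluable, or 100 patisiran and 50 placebo.

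**Precision of the planned coefficient.** By Fisher's z, the 95% half-width around r = 0 is tanh(1.96 / √(n − 3)): 0.196 at n = 100 and 0.278 at n = 50.

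**Assumptions.** Let a be the correlation of a baseline factor with Day 22 TTR reduction, b its correlation with mNIS+7 change, and p the partial correlation given that factor. The documents give none of these, so a range is shown. Signs are schematic; only whether the confounding reinforces or opposes the relation matters.

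**Formula.** Raw r = p × √[(1 − a²)(1 − b²)] + a × b.

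- No true relation (p = 0): raw r = a × b, so 0.3 × 0.3 = 0.09.
- True relation masked (p = 0.30, a = 0.3, b = −0.3): 0.30 × 0.91 − 0.09 = 0.183.
- No link to TTR reduction (a = 0, p = 0.30): 0.30 × √(1 − 0.3²) = 0.286, or 0.30 × √(1 − 0.5²) = 0.260.

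**How often the interval excludes zero, n = 100.** For raw r = 0.09, atanh(0.09) × √97 = 0.889, and Φ(0.889 − 1.96) + Φ(−0.889 − 1.96) = 14.4%. For a = b = 0.1, raw r is 0.01 and the same formula gives 5.1%. Simulation with 20,000 replicates per row gives:

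| a | b | p | raw r (formula) | raw interval excludes 0 | adjusted interval excludes 0 |
|---|---|---|---|---|---|
| 0 | 0.3 | 0 | 0 | 4.9% | 4.8% |
| 0.1 | 0.3 | 0 | 0.03 | 6.1% | 5.0% |
| 0.3 | 0.3 | 0 | 0.09 | 14.5% | 5.1% |
| 0.5 | 0.5 | 0 | 0.25 | 71.6% | 5.0% |
| 0.3 | −0.3 | 0.30 | 0.18 | 44.8% | 86.4% |
| 0.5 | −0.5 | 0.30 | −0.02 | 5.7% | 86.3% |
| 0 | 0.3 | 0.30 | 0.29 | 82.8% | 85.9% |
| 0 | 0.5 | 0.30 | 0.26 | 75.1% | 86.1% |

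For confounding alone to produce a coefficient as large as the half-width, a × b must reach 0.196, for example both about √0.196 = 0.44.

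**Cost in precision of adjusting.** Six degrees of freedom: one each for baseline score, genotype, onset age and stabilizer use, and two for three regions. At n = 100 the interval around 0.30 moves from (0.110, 0.469) to (0.104, 0.474).

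**The case against.** The strongest reply is that nothing is being tested. SAP 4.4 asks for a p-value when it correlates the two TTR assays but not here, and SAP 3.2 places formal testing elsewhere. A reader might infer that this correlation is the test of the therapeutic hypothesis and could give the wrong answer on whether the drug works. The documents do not support that: the confirmatory evidence is the randomised MMRM contrast, which is already adjusted. The rates above describe how an interval behaves, not a decision that the plan makes. This part of the objection stands in full.

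A reader might also infer that baseline severity is a known confounder. It is not. Nothing in either document links severity to TTR reduction, and severity is not among the TTR subgroups in SAP 4.4. Those subgroups concern reduction over 18 months rather than at Day 22, and planning a summary is not evidence of an association. For genotype the documents lean the other way: the target region is shared by wild-type TTR and all reported mutations (protocol 1.1.3), and mutant and wild-type TTR fell equally in V30M patients (protocol 1.3). This stands too, so the bias is possible rather than shown.

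Third, a spurious 0.09 lies inside a half-width of 0.196. True, but it is nearly half of it and roughly triples the rate at which the interval excludes zero.

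Last, adjusted exposure-response modelling may exist in the separate report. Its content cannot be seen from these documents, so it cannot be said that no adjusted analysis is planned. What SAP 4.5.2 itself describes is optional, concerns PK exposure and names no covariates, so it does not settle the point for SAP 4.4.

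**Conclusion.** The point holds as a cheap improvement to an exploratory analysis. The coefficient is unadjusted, the quantity correlated is not randomised within an arm, and the plan already holds covariates that it considers relevant to the outcome. The bias could run in either direction, and its size rests entirely on assumed links: about 15% false exclusion of zero if both are 0.3, negligible if both are 0.1, and large only if both approach 0.5. With no link to TTR reduction, a true 0.30 falls only to between 0.26 and 0.29. No primary or secondary result changes. Adjustment would not make the analysis causal; it would only remove confounding by the measured factors and, where those factors predict mNIS+7 change, sharpen the estimate.

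**What to change.** In SAP 4.4, add for the patisiran arm a regression (or partial correlation) of mNIS+7 change at Months 9 and 18 on Day 22 TTR percentage reduction, adjusted for baseline mNIS+7, genotype, age at onset, region and previous stabilizer use. Report the slope with its 95% confidence interval beside the planned Pearson coefficient and scatterplots, and label both as exploratory and observational. Specifying this before unblinding also avoids a later choice between adjusted and unadjusted results.

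The cost is one sentence in the SAP, one extra model per time point and about six degrees of freedom in an arm of about 100 evaluable patients. No new data are needed, and nothing planned is removed.
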